10.2 Prior to Leukapheresis (Vaccine Cell Generation)

- Perform randomization prior to leukapheresis #1.
- CBC with differential and CD4+/CD8+ T cell ratio.
- Comprehensive metabolic panel
- For females of child-bearing potential, β -HCG serum pregnancy test.
- Infectious disease testing in accordance with institutional practices.
- Blood for immune monitoring.
- Dialysis type central venous catheter for patients with poor venous access.
- Oral Tums, 2 tablets, BID for 2 days prior to the leukapheresis procedure (if standard-of-care) to prevent the development of hypocalcemia from the citrate.
- Document adverse events.
- Document concomitant medications.

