10.4 Adjuvant TMZ Cycles

- History, physical & neurological exam
- Confirm eligibility prior to TMZ cycle 1.
- Administer Td booster with vaccine 1.
- Administer TMZ.
- Administer study vaccines.
- Perform vaccine site pretreatment with Td (1Lf) or saline intradermal prior to Vaccine #3, #6, and #9.
- Inguinal MRI/MRS imaging with Vaccine 3 (University of Florida site only). For women of childbearing potential a urine pregnancy test will be obtained prior to imaging.
- Blood for immune monitoring:
 - Leukapheresis 1
 - Prior to vaccine 1
 - Prior to vaccine 2
 - Prior to vaccine 3
 - At MRI/MRS imaging time points (UF site only)
 - Leukapheresis 2
 - Prior to vaccine 4
 - Prior to vaccine 7
 - Prior to vaccine 10

- At progression
- Urine for immune monitoring
 - Prior to vaccine 1
 - At MRI/MRS imaging time points (UF site only)

Patients seen by the neuro-oncology team between these vaccine visits may have blood drawn for immune monitoring at the discretion of the study team.

For immune monitoring, up to 80 mLs of blood will be collected in 10 yellow top tubes and processed in accordance with **SOP-UFBTIP-126**. For humoral response, approximately 3.5 mLs will be collected in a gold top tube.

- CBC with differential and CD4+/CD8+ T cell ratio at each vaccine visit and, if clinically indicated, at routine clinic visits.
- MRI (or CT) at the following time points:
 - bimonthly during TMZ cycles and every 3 months after the 12th TMZ cycle (or 1 year post surgery if TMZ discontinued prior to 12 cycles)
 - Response and progression will be assessed following Modified RANO Criteria as described in Section 11. Response Evaluation. Initial assessment of disease status will be done by the treating neuro-oncologist/study investigators, upon review of surveillance brain MRI during routine clinic visit followed by study vaccine administration or chemo cycle initiation. Clinical assessment of disease status will be followed by formal measurements of enhancing lesions for modified RANO criteria.
- Review and document adverse events at each visit.
- Review and document concomitant medications at each visit.

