- 14 Up to 10 yellow top tubes (ACD-A) and 1 gold top tube (SST) during initial leukapheresis, prior to vaccines 1-3, during second leukapheresis, prior to vaccine 4, 7, 10, at MRI/MRS imaging time points (UF site only) and at progression if feasible. Peripheral blood will be processed in accordance with **SOP-UFBTIP-126**.
- 15 All patients will receive IM Td booster (5 Lf) with vaccine #1.
- 16 2 to 4 weeks after vaccine #3, repeat leukapheresis for DC or PBMC generation.
- 17 All patients will undergo vaccine site pretreatment with Td (1 Lf) or saline 6-24 hours prior to Vaccine #3, #6, and #9.
- 18 Patients at University of Florida site will undergo MRI/MRS imaging of inguinal draining lymph nodes before vaccine #3 site pretreatment, 48hrs post vaccination, and 5 to 7 days post vaccination (optional). Urine samples will be collected prior to vaccine #1 and at MRI/MRS imaging time points.
- 19 Within 7 weeks of surgery.
- 20 AE collection will begin at the time of administration of vaccine #1 and continue until 30 days after the last dose of study drug. Any adverse events associated with leukapheresis will also be recorded.
- 21 Including MMSE for patients age \geq 50 years.
- 22 Results from infectious disease markers performed within 30 days of enrollment can be used to satisfy criteria.
- 23 Additional leukapheresis may be performed if needed to generate additional vaccines.

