13.3 Adverse Events

An AE is any untoward medical occurrence associated with use of a drug, whether or not considered drug related. For this protocol, the definition of AE also includes worsening of any pre-existing medical condition. An AE can therefore be any unfavorable and unintended or worsening sign (including an abnormal laboratory finding), symptom, or disease temporally associated with the use of the study drug, whether or not related to use of the study drug. Abnormal laboratory findings without clinical significance (based on the PI's judgment) should not be recorded as AEs. But laboratory value changes that require therapy or adjustment in prior therapy are considered adverse events. Elective and semi-elective surgery in asymptomatic patients should not be recorded as AEs.

An adverse drug reaction is any adverse event caused by a drug. A suspected adverse reaction means any adverse event for which there is a reasonable possibility that the drug caused the adverse event. For the purposes of IND safety reporting, "reasonable possibility" means there is evidence to suggest a causal relationship between the drug and the adverse event.

AE collection will begin at the time of administration of vaccine #1 and continue until 30 days after the last dose of study drug. Grade 2 suspected adverse reactions and all Grade 3 or greater AEs must be recorded in the subject's research record and entered into the OnCore eCRF within 72 hours of PI discovery/notification of the event. Any Grade 3 or greater adverse events associated with leukapheresis will also be recorded. AEs must also be reported to the Coordinating Center as described in 13.3.

AEs will be assessed according to the CTCAE version 5.0 (term and grade) and documented. If CTCAE term does not exist, the PI should select the most appropriate CTC category and indicate "other". If CTCAE grading does not exist for an AE, the severity of the AE will be graded as (1) mild, (2) moderate, (3) severe, (4) life-threatening, or (5) fatal.

Attribution of AEs will be assigned by the PI as follows:

- Definite: The AE is clearly related to the study drug
- Probable: The AE is likely related to the study drug
- Possible: The AE may be related to the study drug
- Unlikely: The AE is doubtfully related to the study drug
- Unrelated: The AE is clearly NOT related to the study drug

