13.5.6 Leukapheresis

As with any donation of blood, a variety of minor reactions may occur with leukapheresis, which include fainting, dizziness, or nausea. Uncommon but serious complications may also result, which include bleeding, infection, an adverse reaction to the anticoagulant or replacement fluids, hypocalcemia, hypotension, shock, convulsions, air emboli, heart failure, or the inability to transfuse blood back into the patient. These risks are reduced by the fact that the procedure will be performed by qualified staff at a specialized clinical hemapheresis unit. Patients will be carefully monitored throughout the procedure by trained nursing and medical staff. Calcium gluconate (2 mg PO) may be given to minimize the risks of hypocalcemia, fluid supplementation may be given to minimize hypotension, and blood will be routinely screened for infectious disease in accordance with institutional practices to minimize the risk of transmitting infection.

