15 STATISTICAL METHODS AND DATA ANALYSIS

15.1 Study Design Overview

The primary goal of this randomized phase II study is to determine whether the addition of pp65-LAMP mRNA DC vaccination in adult patients with newly-diagnosed GBM receiving dose-intensified TMZ will be a treatment worthy of investigation in a large phase III study. A secondary

objective will be examination of the immunologic responses induced by full-length vs short LAMP sequences.

Although this randomized phase II study is comparative, it will not be definitive as the assessment will be conducted with a large false-positive rate. We have included a concurrently followed control arm in the trial design in lieu of a historical control group to ensure that appropriate comparisons can be made without concern that the patients receiving standard treatment differ in prognostic factors or standards of care (Rubinstein, 2009; Ratain and Sargent, 2009; Rubinstein et al., 2005).

We will randomize eligible patients, after enrollment, to one of 3 study arms in which they will receive 21-day TMZ concurrently with one of the following treatments:

Arm #	Vaccine	Skin Preparation
1	pp65-shLAMP mRNA DCs with GM-CSF	Tetanus
2	pp65-fLAMP mRNA DCs with GM-CSF	Tetanus
3	PBMCs	Saline

Randomization will be stratified by:

- Age 69 years old and younger; or 70 years old and older
- RPA Class (III, IV, or V)
- CMV seronegative or seropositive

We will use a permuted block randomization scheme with a 1:1:1 study arm allocation ratio and a block size of 6 within each stratum.

Adapted RPA Stages For Malignant Gliomas (Survival With Concurrent Temozolomide and Radiation Therapy vs Radiation Therapy alone)				
Stage	Characteristics	Median OS	2-year OS	p-value vs. control
III	Age <50, PS 0	21 vs. 15 mo	43% vs. 20%	p<0.0001
IV	Age <50, PS 1-2 Age >=50, Surgery, MMSE >=27	16 vs. 13 mo	28% vs. 11%	p<0.01
V	Age >=50 and either Biopsy only or MMSE <27	10 vs. 9 mo	17% vs. 6%	p=0.05

Approximately 200 patients will be enrolled in the study, randomized and receive “standard-of-care” radiotherapy concurrent with TMZ under the assumption that approximately 120 patients will be vaccinated according to treatment arm.

A Data Sharing Agreement has been established with Immunomic Therapeutics, Inc. and the University of Florida. A Limited Data Set will be sent to evaluate immunogenicity and clinical efficacy of the vaccine products used within this clinical trial (for patients treated at the UF site

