15.3 Analytic Methods

15.3.1 Primary Objective and Secondary Clinical Objectives

We will use Kaplan-Meier survival curves and the log rank test to characterize and compare PFS and OS in patients who received pp65-LAMP mRNA DC vaccine (Arms 1 and 2) and in control patients (Arm 3). PFS is defined as the time between first vaccination and first documentation of either disease progression/recurrence, or death without prior progression/recurrence. Patients remaining alive without disease progression will have PFS censored at last follow-up. OS will be defined as the time between first vaccination and death, and will be censored at the last follow-up if death has not occurred. We will also perform a stratified analysis incorporating the three stratification variables (age, RPA class, and CMV sero-status) using Cox proportional hazards regression. The index day for all of our primary comparisons will be the time of the first vaccination. Because patients who fail to proceed to the first vaccination because of GBM recurrence or for other reasons cannot experience differential effects due to treatment arm membership, we will not perform an intent-to-treat analysis that includes these patients. We will perform an intent-to-treat analysis of OS and PFS that includes patients who begin the vaccination sequence but who do not receive at least three vaccinations because of recurrence or other reasons. OS and PFS times for adequately vaccinated patients who are lost to follow-up will be considered right-censored at the time of loss and will be included in all of our survival comparisons.

All subjects who receive at least one dose of DC vaccine will be considered evaluable for purposes of safety and toxicity.

All subjects who complete chemoRT and receive dose-intense adjuvant TMZ and at least 3 DC vaccines will be considered evaluable for purposes of the primary and secondary endpoints.

The impact of pp65-LAMP mRNA DC vaccine on PFS and OS in patients with gross total resection will also be explored using the log rank test and Kaplan-Meier curves, although our trial design may not necessarily achieve sufficient power to detect a clinically meaningful effect within this patient subgroup.

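### Leukapheresis adverse events are recorded in every patient, but 15.3.1 has no safety set or denominator for patients never vaccinated, and the recording rules before vaccine 1 conflict

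*Combined protocol and SAP*

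**What the plan says.** Section 13.3 sets the general window: "AE collection will begin at the time of administration of vaccine #1 and continue until 30 days after the last dose of study drug". It then adds the leukapheresis exception: "Any Grade 3 or greater adverse events associated with leukapheresis will also be recorded". Footnote 20 of the schedule in 10.7 repeats the window but words the exception more widely: "Any adverse events associated with leukapheresis will also be recorded". Section 10.2, the step before the first leukapheresis, lists "Document adverse events" with no grade limit. Section 10.4, on the adjuvant temozolomide cycles, says "Review and document adverse events at each visit" and names no vaccine-1 start.

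On analysis, 15.3.1 says that subjects with one or more doses of DC vaccine "will be considered evaluable for purposes of safety and toxicity". No other safety set is defined. Section 13.3 also keeps a running summary of all Grade 3 or greater events, sorted by organ system, relationship, grade and outcome.

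On numbers, 15.1 plans for about 200 patients enrolled and randomized "under the assumption that approximately 120 patients will be vaccinated according to treatment arm". Randomization precedes the first leukapheresis (10.2), and vaccine 1 follows randomization by about 15 weeks (15.2). Section 13.5.6 describes the procedure's risks: "Uncommon but serious complications may also result, which include bleeding, infection, an adverse reaction to the anticoagulant or replacement fluids", and its list goes on to shock, air emboli and heart failure. Section 13.5.7 adds pneumothorax and vessel injury for those patients who need a central venous catheter.

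**The concern.** Leukapheresis is done to make the study product, so its harms belong to the regimen that the trial may recommend for phase III. If procedure harms are summarized in the 15.3.1 safety set, the rate is conditioned on having come through the procedure and the following 15 weeks. A patient whose participation ended because of a leukapheresis or catheter complication would be in neither the numerator nor the denominator. The 13.3 summary does not cure this, because it lists events without counting patients or procedures at risk.

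Two wording problems add to it. Catheter events are not named in the recording rules, so they are covered only if they are taken to be associated with leukapheresis. The opening of the window at vaccine 1 also leaves it unclear whether events in the first weeks of adjuvant temozolomide are to be recorded. Expedited reporting in 13.4 is tied to the adverse event reporting periods, so the same uncertainty carries over to serious events in those weeks.

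**Working it through.** **1. Recording compared with analysis.**

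| Place | Covers | Grade | Limited to vaccinated patients? |
|---|---|---|---|
| 10.2 | step before leukapheresis 1 | none stated | no |
| 10.4 | each visit in adjuvant cycles | none stated | no |
| 10.7, footnote 20 | leukapheresis events | any | no |
| 13.3, exception | leukapheresis events | 3 or greater | no |
| 13.3, summary | all events | 3 or greater | no |
| 15.3.1, safety set | evaluable patients | not applicable | yes, and DC vaccine |

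Recording does not depend on vaccination; the safety set does. Footnote 20 and 13.3 disagree on Grade 1 and 2 leukapheresis events.

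**2. Patients outside the safety set.** The plan's 120 is 40 + 40 + 40 (15.2). From 15.1, 200 − 120 = 80, and 80/200 = 40%. This is a ceiling for leukapheresis exposure: the change-log entry for version 20210810 gives screen failure as one reason for raising enrolment to 200. The share is not given. For an assumed share s, the randomized but unvaccinated number is 200 × (1 − s) − 120:
- s = 0: 80 (200 randomized)
- s = 10%: 60 (180 randomized)
- s = 20%: 40 (160 randomized)

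The number leukapheresed is no higher than the number randomized.

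**3. What the denominator does to precision.** With zero events in n patients, the one-sided 95% upper bound is 1 − 0.05^(1/n). The chance of seeing at least one event at true rate p is 1 − (1 − p)^n. The rates of 1% and 2% are assumptions, since the documents give none.

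| n | Set | Upper bound, zero events | p = 1% | p = 2% |
|---|---|---|---|---|
| 80 | Arms 1 and 2 only (literal DC vaccine) | 3.7% | 55% | 80% |
| 120 | vaccinated, all arms | 2.5% | 70% | 91% |
| 160 | leukapheresed, if s = 20% | 1.9% | 80% | 96% |
| 200 | leukapheresed, if s = 0 | 1.5% | 87% | 98% |

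The expected count at 2% is 0.02 × 120 = 2.4 in the vaccinated and 0.02 × 200 = 4.0 in 200 patients. The 2.4 assumes that a complication does not change the chance of being vaccinated; if it lowers that chance, fewer than 2.4 would be seen.

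**4. Temozolomide before vaccine 1.** Dose-intensified temozolomide is taken on days 1 to 21 (9.5), and vaccine 1 is given on days 22 to 24 (9.8). The 13.3 window therefore opens after the first dosing block. Cycle 1 lasts up to 12 weeks (9.5), so about 3 of up to 12 weeks lie outside the window and the rest lies inside it. For those 3 weeks, 10.4 and 13.3 give different instructions.

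**The case against.** The strongest reply is that nothing is lost. The 13.3 sentence is itself an exception that brings leukapheresis events in from outside the window, and footnote 20 and 10.2 support it. None of them is limited to patients later vaccinated, and the Grade 3 or greater summary is not tied to the evaluable set. That stands. A reader might infer that leukapheresis harms in unvaccinated patients go unrecorded; the documents say the opposite. What is missing is the population and denominator for reporting them.

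Three further replies also stand in part.
- A reader might take 80 as the number exposed to leukapheresis and lost. It is only a ceiling, and only some patients need a catheter. The documents do not say how many unvaccinated patients stopped because of the procedure.
- A reader might infer that all cycle 1 temozolomide toxicity is missed, or that patients intolerant of it never enter the safety set. Most of cycle 1 follows vaccine 1. Section 9.8 also lets patients who no longer qualify, most often for chemotherapy intolerance, receive vaccine at the investigator's discretion under full toxicity monitoring. The conflict with 10.4 means that loss of the early events is possible, not established.
- The second leukapheresis follows vaccine 3, so its events are already inside the window and in vaccinated patients. The gap concerns the first procedure, with any extra procedure done before vaccine 1.

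The omission of Arm 3 is probably loose wording. The efficacy-evaluable definition in 15.3.1 also speaks of DC vaccines, and taken literally it would leave no control group.

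**Conclusion.** The point holds as a gap in the analysis plan and a set of conflicting recording rules. Followed as written, 15.3.1 leaves every leukapheresed but unvaccinated patient out of the only stated safety set. That is at most about 80 of 200 patients, or 40 to 80 randomized patients if screen failures make up 20% to 0% of the 200 (an assumed range). The change in the zero-event bound, from 2.5% to between 1.9% and 1.5%, is modest. The more important effect is that procedure safety is conditioned on reaching vaccine 1, and the size of that effect cannot be worked out from the documents.

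The conflicts between 13.3 and footnote 20 on grade, and between 13.3 and 10.4 on when recording starts, are plain from the text. None of this touches the overall survival comparison or the vaccine toxicity stopping boundary in 13.2.

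**What to change.** 1. In 15.3.1, add a procedure-safety set of all patients who undergo leukapheresis. Report leukapheresis and related catheter events per patient and per procedure, by arm, whether or not the patient was vaccinated.
2. Word the vaccine safety set so that it includes PBMC recipients as well as DC recipients.
3. Reconcile 13.3 and footnote 20 on the grade at which leukapheresis events are recorded, and state whether catheter events count among them.
4. Reconcile 13.3 and footnote 20 with 10.4 on when adverse event recording starts, and tabulate events before vaccine 1 separately from later ones.

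The cost is small. Items 1 and 2 are plan wording and a little more tabulation of events already recorded. Items 3 and 4 need a few sentences. If the 10.4 reading is adopted, there are about three weeks of extra event entry per patient, or abstraction from existing visit notes if accrual is over. The documents do not state enrolment status.

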13.4 Adverse Event and Serious Adverse Event (SAE) Reporting

All adverse events grade 2 or greater where there is evidence to suggest a causal relationship (possible, probable or definite) between the AE and investigational drug or study participation and all serious adverse events (regardless of causality) occurring at participating sites during the AE reporting periods require expedited reporting to the Coordinating Center.

Adverse events meeting the definition of an SAE and any grade 2 or greater AEs where there is a possible, probable or definite relationship between the AE and investigational drug must be reported to the Coordinating Center within 24 hours of the investigator's discovery. Initial notification may be via e-mail. A formal written initial report using **UFBTIP Serious Adverse (SAE) Report** must be sent to the Coordinating Center per the reporting timeframes outlined above. SAEs and AE requiring expedited reporting must be entered into the OnCore eCRF as soon as possible but no later than 72 hours after discovery.

All other AEs grade 3 or greater will be documented in the OnCore database for Protocol Chair review during the investigation.

The Protocol Chair will promptly review expedited investigator reports and communicate the AE assessment to the reporting investigator and IND sponsors, as applicable. If the AE meets FDA reporting requirements as described in 13.3.2, site PIs and IND sponsors will be notified and the IND sponsors will be responsible for reporting to FDA under the INDs regardless of which site initially reported the AE.

If a death occurs within 30 days of DC vaccine administration, that is not attributable to progressive disease or other obvious non-study related cause (i.e. motor vehicle accident), enrollment of new subjects will be suspended until review by the Protocol Chair and IND Sponsor has been completed and the FDA notified. If attribution of death is determined by the Protocol Chair, IND Sponsor or FDA to be possibly, probably or definitely related to trial drug, continued treatment of all enrolled subjects with trial drug will be suspended until the review is completed and recommendations for study continuation have been issued and approved by FDA. Any death attributed to trial drug, regardless of the timeline with respect to last treatment, will result in suspension of enrollment and suspension of continued treatment for enrolled subjects until review by FDA is complete, and recommendations for study continuation issued and approved. The IRB and DSMB will be notified of subject deaths per local policy. Deaths or life-threatening adverse events will be reported to FDA by the IND sponsors as soon as possible but no later than 7 calendar days after the sponsor's initial receipt of the information (21 CFR 312.32).

Grade	Relation to IP	Report to Coordinating Center	Report to IRB and DSMB	Report to FDA
AE Grade 3	No	Enter data in OnCore	Report per local policy	No
AE \geq Grade 2	Possible, probable or definite	Report within 24 hours via email	Report per local policy	IND sponsor will report to FDA if

				meets definition below
SAE	All	Report within 24 hours via email	Report per local policy	IND Sponsor will report to FDA within 15 calendar days if meets FDA requirement
Fatal or life threatening	All	Report within 24 hours by phone and via email	Report per local policy	IND Sponsor will report to FDA within 7 calendar days if meets FDA requirement

